7.5.2.1 Liver Abnormalities

The following potentially clinically significant criteria in liver function tests for Alkaline Phosphatase (ALP), Alanine Transaminase (ALT), total bilirubin, Aspartate Transaminase (AST) and their combination are defined. The subject's highest value during the investigational period will be used.

Parameter	Criteria
ALT	> 3xULN
	> 5xULN
	> 10xULN
	> 20xULN
AST	> 3xULN
	> 5xULN
	> 10xULN
	> 20xULN
ALT or AST	> 3xULN
	> 8xULN
Total Bilirubin	> 2xULN

ALP	> 1.5xULN
ALT and/or AST OR Total Bilirubin(*)	(ALT and/or AST > 3xULN) or total bilirubin > 2xULN
ALT and/or AST AND Total Bilirubin(*)	(ALT and/or AST > 3xULN) and total bilirubin > 2xULN

(*) Combination of values measured within same sample

The number and percentage of subjects with potentially clinically significant values in liver function tests during the investigational period will be presented by treatment group.

Additionally, confirmed liver abnormalities will be characterized as moderate and marked, as follow:

Moderate: ALT or AST > 3×ULN OR Total Bilirubin > 2×ULN.

Marked: ALT or AST > 3×ULN AND Total Bilirubin > 2×ULN.

Number and percentage of subjects in each category at each scheduled visit will be summarized. These combinations of elevated values are based on measured value within the same sample.

Liver Functions Plots

A matrix scatter plot of liver function test will be plotted showing the maximum ALT, AST, ALP and total bilirubin during study period crossed against each other. Different dots will be used for randomization arm.

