6.2 Safety Variables

- AEs
- Vital signs (body temperature, pulse rate and blood pressure in sitting position)
- Body weight
- 12-lead ECG
- Central ECG
- Chest radiography
- Laboratory assessments

Treatment emergent adverse events (TEAEs) will be defined as any adverse event that started or worsened in severity after initial dose of study drug or reference drug through Week52 or Withdrawal.

AE for the subjects who switched ASP015K 100 mg or ASP150 mg from Placebo at Week 12 will be handled as follows:

- AE onset before the first dose of week12 study drug will be considered to be occurred at Placebo.
- AE onset after the first dose of week12 study drug will be considered to be occurred at ASP015K 100 mg or 150 mg, which is switched treatment from Placebo.

A drug-related TEAE is defined as any TEAE with possible, probable or missing relationship to study drug or reference drug as assessed by the investigator.

Moreover, any TEAE with missing relationship to study drug or reference drug was counted as drug related (probable).

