- 100 mg: subjects who initially treated as ASP015K 100 mg Group
 - 150 mg: subjects who initially treated as ASP015K 150 mg Group
 - Placebo to 100 mg at Week 12: subjects who initially treated as Placebo group and switched ASP015K 100 mg at Week 12 and at least one dose of ASP015K 100 mg drug after switched
 - Placebo to 150 mg at Week 12: subjects who initially treated as Placebo group and switched ASP015K 150 mg at Week 12 and at least one dose of ASP015K 150 mg drug after switched
 - Etanercept: subjects who initially treated as Etanercept Group
- MedDRA11.1 will be used as the coding dictionary for adverse event and medical history.

- Statistical hypothesis testing will be performed only if specified. All statistical comparisons of treatment groups will be versus placebo (i.e., each ASP015K treatment versus placebo) and will be made using two sided tests at the 0.05 significance level, unless stated otherwise. Multiplicity adjustment will be done in the primary analysis and other analysis if specified.
- Statistical analysis including hypothesis testing for efficacy variables to compare ASP015K 100 mg or ASP015K 150 mg versus Placebo, only the data for the pairwise comparison will be used.
- All statistical results will be presented, as appropriate, by treatment group, by treatment group and scheduled visit; the schedule of assessments is provided in Section 7.11.5-7.
- Demographics and other baseline characteristics will be provided for all ASP015K treatment groups combined ("100 mg + 150 mg") and for all treatment groups, including placebo and reference group, combined ("Total"). Efficacy presentations will not contain combined treatment groups. In study drug exposure, pharmacodynamics and safety presentations, "Total except for Etanercept" will be used in place of "Total".
- Chi-square test is continuity corrected in all analysis.
- Confidence interval for binary outcome is continuity corrected in all analysis.
- Baseline for safety is defined as last non-missing value before the first dose of study drug or reference drug for all subjects including placebo or reference group assigned subjects.
- The values below the lower limit of quantitation (BQL) for β -D-glucan, hCG, Troponin, CK-MB will be treated as it is and these variables are not used for descriptive statistics and displayed in the listings. As for β -D-glucan, it is used for shift-from baseline analysis.

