7.11.6 Handling of Schedule of Assessments of Safety Variables

For data obtained after the end of study treatment, the data obtained within + 2 days after the last dose is taken will be included in analysis. For data after the end of reference treatment, data obtained within + 9 days after the last dose will be included in analysis. Baseline for safety is defined as last non-missing value before the first dose of study drug or reference drug for all subjects including placebo assigned subjects. For Week 12/ET, the values at closest date to reference date will be used. As for the subjects who switched to receive ASP015K instead of placebo, the last observation before first dose of ASP015K at Week 12 will be used for the analysis for visit Week 4, 8, 12, 12/ET. For EOT, the closest value to the reference date will be used regardless of the switching from placebo.

- (1) Physical examination, vital signs, laboratory test [hematology, biochemistry, urinalysis, and pregnancy test (serum and urine)]

Table 12. Visit Window for Physical examination, vital signs, laboratory test (hematology, biochemistry, urinalysis, and pregnancy test (serum and urine))

Time points defined in analysis	Reference date*	Acceptable time range
Screening	Day -28 to Day -1	Day -28 to Day -1
Baseline	Day 1	Day 1
Week 4 to Week 48**	Day $7 \times x + 1$	Day $(7 \times x - 6)$ to Day $(7 \times x + 8)$ and before the initiation of treatment with the study drug or reference drug on the visit day
Week 52	Day 365	Day 358 to Day 372
Minimum on Treatment up to Week 12***		Minimum value at allowance Range (Day 2 to Day 92) before first dose of Week 12 study drug
Maximum on Treatment up to Week 12***		Maximum value at allowance Range (Day 2 to Day 92) before first dose of Week 12 study drug
Minimum on Treatment***		Minimum value during Entire Period (No limitation for period)
Maximum on Treatment***		Maximum value during Entire Period (No limitation for period)
Week 12/ET (Week 12 or at early termination before Week 12)	Day 85	Day 2 to Day 92
EOT (Week 52 or at early termination)	Day 365	Day 2 to Day 372

*: Day 1 represents the first day of study or reference treatment. The day before the initiation of treatment with the study drug or reference drug is expressed as Day -1.

** : Represents the reference date and acceptable time range for Week x.

***: Applied to laboratory test only.

(2) Laboratory test (fasting lipid profile test)

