Alanine Aminotransferase (ALT)	X1 ^{#1}	X2 ^{#1}
Alkaline Phosphatase (ALP)	X1 ^{#1}	X2 ^{#1}
Total Bilirubin Category 1	X1 ^{#1}	X2 ^{#1}
Total Bilirubin Category 2	X1 ^{#1}	X2 ^{#1}
Low-Density Lipoprotein (LDL) Category 1	X1 ^{#1}	X2 ^{#1}
Low-Density Lipoprotein (LDL) Category 2	X1 ^{#1}	X2 ^{#1}
Hemoglobin (HGB) Category 1	X1 ^{#1}	X2 ^{#1}
Hemoglobin (HGB) Category 2	X1 ^{#1}	X2 ^{#1}
Hemoglobin (HGB) Category 3	X1 ^{#1}	X2 ^{#1}
Creatine Phosphokinase (CPK) Category 1	X1 ^{#1}	X2 ^{#1}
Creatine Phosphokinase (CPK) Category 2	X1 ^{#1}	X2 ^{#1}
Creatine Phosphokinase (CPK) Category 3	X1 ^{#1}	X2 ^{#1}
Creatinine	X1 ^{#1}	X2 ^{#1}
Absolute Neutrophil Count (ANC)	X1 ^{#1}	X2 ^{#1}
Lymphocytes Category 1	X1 ^{#1}	X2 ^{#1}
Lymphocytes Category 2	X1 ^{#1}	X2 ^{#1}
Platelets Category 1	X1 ^{#1}	X2 ^{#1}
Platelets Category 2	X1 ^{#1}	X2 ^{#1}
Shift-from-Baseline Table for Selected Laboratory Variables using NCI-CTCAE Toxicity Grade (version 4.0) Baseline to Week 12/ET /EOT	X1	X3

Liver Function Analysis up to Week 12/ for Overall Period	X1 ^{#1}	X2 ^{#1}
Clinically Significant Values in Liver Function Tests	X1 ^{#1}	X2 ^{#1}
Summary of Moderate and Marked Liver Abnormalities by Visit	X1 ^{#1}	X2 ^{#1}
Liver Functions Plots	X1 ^{#1}	X2 ^{#1}
Vital Signs		
Vital Signs Actual and Change from Baseline	X1	X2
ECG Results		
Interpretation of 12- Lead ECG Results, Assessment by Investigator Shift-from-Screening Table for 12-Lead ECG	X1	X2

X1: Placebo, 100mg, 150mg, Reference

X2: 100mg, 150mg, Placebo to 100 mg at Week 12, Placebo to 150 mg at Week 12, Reference

X3: 100mg, 150mg, Reference

#1: Subgroup analysis based on study region will be also presented.

#2: Subgroup analysis based on study region will be presented only.

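### The overall-period liver table classifies placebo switchers by a maximum that spans placebo and ASP015K, so it cannot show which treatment an abnormality arose on; the liver plot's labelling instructions conflict

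*SAP*

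**What the plan says.** **Liver table.** SAP 7.5.2.1 lists limits for ALT, AST, bilirubin and ALP and adds: "The subject's highest value during the investigational period will be used". The laboratory window in SAP 7.11.6, Table 12, agrees: "Maximum value during Entire Period (No limitation for period)".

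**Groups.** Table 23 (SAP Appendix 4) has a row headed "Liver Function Analysis up to Week 12/ for Overall Period". Up to Week 12 it uses the initial arms (X1). For the overall period it uses X2, defined as: "X2: 100mg, 150mg, Placebo to 100 mg at Week 12, Placebo to 150 mg at Week 12, Reference".

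**Liver plot.** SAP 7.5.2.1 plots maximum ALT, AST, ALP and bilirubin over the study period against each other and says: "Different dots will be used for randomization arm". Table 23 assigns the overall plot to X2. SAP 7.5 assigns non-AE safety analyses up to Week 52 to the Treatment Sequence Set.

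**Table 7 ranges.** The text of SAP 7.5.2 counts each subject's highest or lowest value up to Week 12 or over the entire period. Table 23 lists the same categories by visit, in X1 and X2.

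**Treatment of the switch elsewhere.** For adverse events, SAP 6.2 says: "AE onset after the first dose of week12 study drug will be considered to be occurred at ASP015K 100 mg or 150 mg". For laboratory values up to Week 12, Table 12 uses: "Maximum value at allowance Range (Day 2 to Day 92) before first dose of Week 12 study drug". No matching maximum is defined for the time after the switch.

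**The concern.** Evaluating 52-week safety is a stated objective, and subjects who start ASP015K at Week 12 contribute to it. The usual question for these subjects is how many crossed a liver limit after starting the drug. The overall liver table cannot answer it, because one peak over the whole period decides the category and the placebo weeks are included. A count in a switch column therefore mixes background abnormality on placebo with anything that arose on ASP015K.

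The plot raises a related problem. Read literally, marking by randomised arm would show a switcher's peak on ASP015K as a placebo dot. Because the plot crosses separate maxima, one dot could also pair an ALT peak on placebo with a later bilirubin peak on ASP015K.

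**Working it through.** The plan gives no figure for this point, so there is none to reproduce. The check is a comparison of passages followed by an illustration of size.

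**Step 1. Which overall-period outputs mix exposure in switchers?**

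| Output | Value used | Overall-period groups | Placebo weeks mixed in? |
|---|---|---|---|
| Liver limits (SAP 7.5.2.1) | Highest, no period limit | X2, switchers included | Yes |
| Moderate/marked liver abnormality | Each scheduled visit, same sample | X2 | No, the visit shows it |
| Table 7 ranges | Entire period (7.5.2) or by visit (Table 23) | X2 | Yes on the first reading, no on the second |
| Shift to highest/lowest | Highest/lowest | X3 (100 mg, 150 mg, reference) | No, switchers not included |
| Toxicity-grade shift | Worst value | X3 | No, switchers not included |
| Liver plot | Study-period maximum | Randomised arm (7.5.2.1) or X2 (Table 23) | Yes on either reading |

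The overall liver limits pair a sequence grouping with an uncut maximum. By contrast, the adverse event overview (Table 20) uses X2 only for the period from Week 12 onward and X3 for the overall period.

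**Step 2. How much of a switcher's record is on placebo?** The Schedule of Assessments has biochemistry every 4 weeks from Week 4 to Week 52, which is 13 scheduled post-baseline visits. Samples from Week 4 to Week 48 are taken before dosing on the visit day, so Weeks 4, 8 and 12 are placebo values.

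- Visits: 3/13 = 23%
- Weeks: 12/52 = 23%

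**Step 3. Illustration.** Let q be the probability per visit of crossing a limit on placebo, and k the ratio of that probability on ASP015K. Visits are treated as independent. Both q and k are assumptions.

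- Any abnormality on placebo: A = 1 − (1 − q)^3
- Any abnormality after the switch: B = 1 − (1 − kq)^10
- Any abnormality overall: T = 1 − (1 − q)^3 (1 − kq)^10
- Share of flagged switchers abnormal on placebo only: A(1 − B)/T

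For q = 0.5% and k = 1: A = 0.0149, B = 0.0489, T = 0.0631, and the share is 0.0149 × 0.9511/0.0631 = 22.5%.

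Take 50 subjects per switch column, which assumes that the 100 planned placebo subjects split evenly and that none leave before Week 12. The expected number flagged is then 50 × 0.0631 = 3.15 with the uncut maximum and 50 × 0.0489 = 2.44 with a post-switch maximum.

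| k | Placebo-only share, q = 0.25% to 2% | Flagged of 50 at q = 0.5%: uncut / post-switch |
|---|---|---|
| 1 | 22.8% to 20.8% | 3.15 / 2.44 |
| 2 | 12.7% to 10.4% | 5.46 / 4.78 |
| 3 | 8.7% to 6.4% | 7.66 / 7.01 |

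At q = 0.5% the excess is under one subject per column. At q = 2% and k = 1 it is 11.55 − 9.15 = 2.40.

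**Step 4. Plot window.** The SAP's key terms start the study period at informed consent, so a plotted maximum could be a screening value taken before any treatment.

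**The case against.** The best defence is that the damage is contained. Switchers sit in columns whose headings state the sequence, and SAP 7.1 describes those groups as optional and outside the primary objective. Moderate and marked liver abnormalities are tabulated by visit, and the marked category requires raised transaminase and bilirubin in the same sample, so a scheduled case can be placed before or after the switch. Placebo-period results are reported separately up to Week 12. Hy's Law cases are handled as serious adverse events (Protocol Appendix 3), and adverse events are split at the switch.

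All of that stands and limits the consequence. It does not supply the missing count: no worst-value summary tells the reader how many switchers ever crossed a liver limit after starting ASP015K.

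Four stronger readings are tempting, and the documents do not support them:

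- **All overall worst-value laboratory tables are affected.** They are not. The shift and toxicity-grade tables leave switchers out.
- **Placebo abnormalities are reported as ASP015K abnormalities.** They appear in a mixed-exposure column labelled as such. The 100 mg and 150 mg columns contain no placebo values.
- **The plot definitely mislabels switchers.** Table 23 places the overall plot in the sequence groups. In addition, the Week 12 dose is itself allocated at random at baseline, so the wording in 7.5.2.1 could be read to include the sequence. This is a conflict between passages, not an established error.
- **The safety baseline is wrong for switchers.** The SAP chose one rule deliberately: "Baseline for safety is defined as last non-missing value before the first dose of study drug or reference drug for all subjects including placebo". A Week 12 baseline would be a preference.

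**Conclusion.** The point holds for the overall-period liver table. As written, its counts for the two switch sequences cannot be attributed to placebo or to ASP015K, because 3 of 13 scheduled visits (23%) precede any ASP015K and no cut is applied. It holds for the Table 7 ranges only if the entire-period reading in SAP 7.5.2 is followed rather than the by-visit listing in Table 23. For the plot, what is established is a contradiction about labelling and a window that opens too early.

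The size is modest. The placebo-only share of flagged switchers is about 21% to 23% with no drug effect and falls to about 6% to 13% if ASP015K doubles or triples the risk. These figures rest on assumed per-visit risks, independence between visits and, for the counts, an even split of switchers that the documents do not state. The primary analysis is untouched. The correction is still worthwhile, because the affected outputs serve to detect a liver signal.

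**What to change.** 1. In SAP 7.11.6, Table 12 (and Table 13 for LDL), define a post-switch maximum and minimum for SEQ3 and SEQ4, using only samples after the first Week 12 dose of ASP015K. The existing maximum up to Week 12 already covers the placebo weeks.
2. Use the post-switch values for SEQ3 and SEQ4 in the overall liver table and in any entire-period Table 7 summary. Make SAP 7.5.2 and Table 23 agree on whether Table 7 is run by visit, over the entire period, or both.
3. In the liver plot, show placebo maxima up to the pre-dose Week 12 sample and ASP015K maxima after it. Replace the labelling sentence in SAP 7.5.2.1 so that it agrees with Table 23, and start the window after the first dose.
4. Keep the single safety baseline. A Week 12 baseline for the baseline-relative limits is optional.

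The cost is a few lines of SAP text and a date filter of the kind already specified for adverse events and for the Week 12 maximum. The drawback is shorter observation in the switch columns: 10 scheduled visits instead of 13.

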7.5.3 Vital Signs

Raw values and changes from baseline at each scheduled visit will be summarized using descriptive statistics.

7.5.4 Electrocardiograms (ECGs)

<12-lead ECG>

- Raw values (categorical) and changes from baseline (shift from baseline) will be summarized, and the summaries will include number and percentage of subjects with normal, not clinically significant abnormal and clinically significant abnormal 12 lead ECG findings.

<Central ECG (except for reference group)>

QTc intervals should be calculated by followed procedure:

- Bazett's formula: $QTc = QT/(RR/1000)^{1/2}$

- Fridericia's formula: $QTc = QT/(RR/1000)^{1/3}$

Change for ECG variables is defined in two ways.

- baseline: before the first dose of study drug or reference drug
 - pre-dose at Week 4 / Week 8: before the Week 4 / Week 8 dose of study drug or reference drug
 - post-dose at Week 4 / Week 8: after the Week 4 / Week 8 dose of study drug or reference drug
- Descriptive statistics of the central ECG variables (QTcF, QTcB, QT, PR, RR intervals, QRS and HR) and the corresponding changes from baseline by each visit and time of measurement will be calculated. In addition, the corresponding changes from pre-dose to post-dose at Week 4 / Week 8 will be calculated.
 - The QT, QTc interval variables will be summarized by the frequencies of subjects with following categories up to Week 12, and each time points.
 - < 300 msec
 - < 330 msec
 - < 360 msec
 - > 450 msec
 - > 480 msec
 - > 500 msec
 - The change from baseline of QT, QTc interval variables will be summarized by the frequencies of subjects with following categories up to Week 12, and each time points. In addition, the corresponding changes from pre-dose to post-dose at Week 4 / Week 8 will be calculated.
 - > 30 msec increase
 - > 60 msec increase
 - > 30 msec decrease
 - > 60 msec decrease

7.5.5 Chest radiography

Chest radiography will be provided as a subject listing only.

7.5.6 Pregnancies

Pregnancies will be provided as a subject listing only.

7.6 Analysis of PK

Refer to PK SAP.

7.7 Analysis of PD

Following analysis is executed for PDAS.

Raw values and changes from baseline for Vascular Endothelial Growth Factor (VEGF), Matrix metalloproteinase 3 (MMP-3) will be summarized using descriptive statistics.

As for Lymphocytes subset variables, as described in 7.5.2, harmonization among each region (Japan, Korea, Taiwan) was reported to be difficult and therefore, Raw values and changes from baseline will be summarized by Study Region (Japan, Korea, Taiwan), using descriptive statistics. For CD3, CD8, CD4, CD19, CD4/CD8 ratio, (CD16 or CD56)+, CD16+ and CD56+, CD16- and CD56+, CD16+ and CD56-, CD16- and CD56-, count values (cells/uL) will be summarized by whole population for exploratory analysis.

1. Japan

- CD3+/Lymphocytes (%), CD3+ (cells/uL)
- CD8+/Lymphocytes (%), CD8+ (cells/uL)
- CD4+/Lymphocytes (%), CD4+ (cells/uL)
- CD19+/Lymphocytes (%), CD19+ (cells/uL)
- CD4/CD8 Ratio
- (CD16 or CD56+)/Lymphocytes (%), (CD16 or CD56)+ (cells/uL)
- (CD16+ and CD56+)/CD3- (%), CD16+ and CD56+ (cells/uL)
- (CD16- and CD56+)/CD3- (%), CD16- and CD56+ (cells/uL)
- (CD16+ and CD56-)/CD3- (%), CD16+ and CD56- (cells/uL)
- (CD16- and CD56-)/CD3- (%), CD16- and CD56- (cells/uL)
- CD56 bright/CD3- (%), CD56 bright (cells/uL)
- CD56 dim/CD3- (%), CD56 dim (cells/uL)

2. Korea

- CD3+/Lymphocytes (%), CD3 (cells/uL)
- (CD3+ and CD8+)/CD3+ (%), CD3+ and CD8+ (cells/uL)
- (CD3+ and CD4+)/CD3+ (%), CD3+ and CD4+ (cells/uL)
- (CD16 or CD56+)/CD3- (%), (CD16 or CD56)+ (cells/uL)
- CD19+/CD3- (%), CD19+ (cells/uL)
- CD4/CD8 Ratio
- (CD16+ and CD56+)/CD3- (%), CD16+ and CD56+ (cells/uL)
- (CD16- and CD56+)/CD3- (%), CD16- and CD56+ (cells/uL)

- (CD16+ and CD56-)/CD3- (%), CD16+ and CD56- (cells/uL)
- (CD16- and CD56-)/CD3- (%), CD16- and CD56- (cells/uL)

3. Taiwan

- CD3+/Lymphocytes (%), CD3 (cells/uL)
- (CD3+ and CD8+)/Lymphocytes (%), CD3+ and CD8+ (cells/uL)
- (CD3+ and CD4+)/Lymphocytes (%), CD3+ and CD4+ (cells/uL)
- (CD16 or CD56+)/Lymphocytes (%), (CD16 or CD56)+ (cells/uL)
- CD19+/Lymphocytes (%), CD19+ (cells/uL)
- CD4/CD8 Ratio
- (CD16+ and CD56+)/Lymphocytes (%), CD16+ and CD56+ (cells/uL)
- (CD16- and CD56+)/Lymphocytes (%), CD16- and CD56+ (cells/uL)
- (CD16+ and CD56-)/Lymphocytes (%), CD16+ and CD56- (cells/uL)
- (CD16- and CD56-)/Lymphocytes (%), CD16- and CD56- (cells/uL)

7.8 Subgroups of Interest

7.8.1 Subgroup analysis of primary endpoint and treatment emergent adverse events

Primary efficacy endpoint and treatment emergent adverse events will be summarized by the treatment group for the subgroups defined on the basis of the categorized variables listed below:

- Sex (Male, Female)
- Age Group (< 65 years, ≥ 65 years)
- Prior Anti-TNF DMARD Use (User, Non-user)
- Prior Biologic DMARD-IR (No, Yes)
- Duration of RA (years)(< 5 years, ≥ 5 years)
- Number of Prior DMARDs Used (0, 1, 2, ≥ 3)
- Number of Prior Biologic DMARDs Used (0, 1, 2, ≥ 3)
- MTX Dose (mg/week) at Baseline (None, 0 mg/week, 0 <- 8 mg/week, 8 <- 12 mg/week, > 12 mg/week)
- Concomitant Steroid at Baseline (No, Yes)
- Prednisone Dose (mg/day) at Baseline (None, 0 <- 5 mg/day, > 5 mg/day)
- Concomitant DMARD at Baseline Use (No, Yes)
- Study Region (Japan, Korea, Taiwan)
- Baseline DAS28-CRP (≤ 3.2, 3.2 <- 5.1, > 5.1) *
- Baseline DAS28-ESR (≤ 3.2, 3.2 <- 5.1, > 5.1) *
- Baseline CRP (< 1.0, ≥ 1.0) *

- Concomitant DMARD Category at Baseline (MTX, DMARD except for MTX only, None)
- Protocol Version Number (used for confirmation of the Inclusion criteria and the Exclusion criteria) (\leq Version 2.0, \geq Version 3.0)
- Body Weight (kg) at Screening ($<$ - 40 kg, 40 kg $<$ - 60 kg, 60 kg $<$ - 80 kg, $>$ 80 kg)

*: Only applied to efficacy analysis.

